## 4 SAMPLE SIZE DETERMINATION

A total of 248 subjects will be randomly assigned in a 1:1 ratio such that 124 subjects will be included in each of the 2 treatment arms. The study is powered at 90% with 179 death events required to detect a HR of 0.59, which corresponds to a 41% reduction in the risk of death, and an approximately 69% increase in median survival compared with a placebo median survival of 20 months, and uses a 1-sided log-rank test, with an alpha of 0.0125, a 1:1 randomization ratio, and an interim OS non-binding futility analysis with boundary of HR = 1.0 at 67% of information time (120 death events from the 179 required death events for the final OS analysis). A total of 248 subjects will yield the 179 events required, under the assumption of 24 months for enrollment (25% of subjects enrolled in the first year and 75% of subjects enrolled in the second year) plus 42 additional months of follow-up.

With 141 PFS events, the study is powered at 90% to detect a HR of 0.55, which corresponds to a 45% reduction in the risk of PFS events (either disease progression or death), and an approximately 82% increase in median PFS compared with a placebo median PFS of 4 months, and uses a 1-sided log-rank test, with an alpha of 0.0125, and a 1:1 randomization ratio.

## 5 STUDY ENDPOINTS

### 5.1 Efficacy Endpoints

#### 5.1.1 Primary Efficacy Endpoint

Two primary efficacy endpoints of PFS by investigator's assessment and OS will be compared between CMB305 and placebo.

##### 5.1.1.1 Progression-free Survival (PFS)

PFS by investigator's review will be the primary endpoint. PFS by investigator's assessment is defined as the time from randomization to the investigator-determined (using RECIST v1.1) date of disease progression or death, whichever comes first:

[PFS = investigator-determined PD date or death date – randomization date + 1].

Investigator-determined PD event includes the followings:

- Disease progression per RECIST v1.1
- Symptomatic deterioration (global health deterioration) as described by RECIST v1.1
- For subjects with NED at time of randomization, any new malignant lesion that occurs after randomization per RECIST v1.1

PFS will be right-censored based on Table 3 for subjects who meet the following conditions:

**Table 3: Censoring Rules for PFS Analysis**

Situation	Date of Censoring	Outcome
No investigator-determined PD or death at the time of study discontinuation	Date of last adequate tumor assessment with no evidence of PD on or before study discontinuation	Censored
Investigator-determined PD or death after 2 or more consecutive missed tumor assessments	Date of last adequate tumor assessment with no evidence of PD that is before the first missed assessment	Censored
Investigator-determined PD or death after the start of subsequent intervention	Date of last adequate tumor assessment with no evidence of PD that is before the first subsequent intervention	Censored
No baseline and/or adequate post baseline tumor assessments or death at time of study discontinuation	Date of randomized	Censored

\* Adequate tumor assessment: tumor assessments with CR, PR, or SD as overall tumor response.

PFS by independent radiological review, if required, will be the supportive endpoints and follow similar definition and censorship as PFS by investigator's assessment, except that only PD from independent radiological review will be included as PD (symptomatic deterioration and clinical PD will not be included as PD).

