- The EE set consists of all subjects without major protocol violations, who have received at least 1 dose of study drug, and have the baseline and at least 1 post-baseline tumor assessment available. The EE set will be analyzed according to the treatment received. Efficacy analyses performed in the EE set will be considered to be supportive.
- The Safety set consists of all subjects taking any amount of study drug. The Safety set is the primary set for safety analyses including AEs and clinical laboratory data. Study treatment exposure also will be summarized using the Safety set. Analyses performed in the Safety set will be considered to be supportive.

Primary Efficacy Analyses:

The 2 primary efficacy endpoints of PFS and OS will be compared between CMB305 and placebo. OS is defined as the time from randomization to the date of death. PFS by investigator's assessment is defined as the time from randomization to the investigator-determined (using RECIST v1.1) date of disease progression or death. Radiographic images will be collected and assessed using RECIST v1.1 until the time the subject begins a new line of treatment.

For the purpose of the PFS analysis, any one of the following events, whichever occurs first, will be used:

- Disease progression per RECIST v1.1 (See Appendix 1, [Table 7 \[Eisenhauer 2009\]](#))
- Symptomatic deterioration (global health deterioration) as described by RECIST v1.1
- For subjects with NED at the time of randomization, any new malignant lesion that occurs after randomization per RECIST v1.1 (See Appendix 1, [Table 8.](#))

Otherwise, subjects who do not have disease progression or have not died will be censored at the date when the last tumor imaging assessment determines a lack of progression. If a subject begins a new anti-cancer therapy or has radiotherapy, surgery, or other local regional therapy at a lesion site prior to documented progression, the subject will be censored at the last assessment where the subject was documented as progression free prior to the intervention. Subjects with 2 or more missing response assessments (except for subjects with symptomatic deterioration) prior to a visit with documented progression (or death) will be censored at the last visit where the subject was documented to be progression free. Progression-free survival by investigator's assessment, will be the primary PFS analysis. Progression-free survival by independent radiological review will be the supportive analysis.

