6.3.1.3 Imaging During Treatment to the Time of Disease Progression

Tumor imaging assessments will be performed and evaluated every 8 weeks after Day 1 until investigator-determined PD (using RECIST v1.1) is documented. Disease progression will be assessed by the investigator using RECIST v1.1. For each subject, the images obtained during the Treatment period must have been collected using the same imaging method for all images during the Pre-screening and Screening periods. Subjects who have a global deterioration of health status that is attributed to progressive disease and leads to discontinuation of study treatment, but who are unable to provide radiographic evidence of disease progression (symptomatic deterioration), will be considered as having PD at the time of documented global deterioration of health for the purpose of determining PFS. Radiographic images (e.g., CT scan or MRI) will also be submitted to an IRC for storage and will be available for evaluation by a central reader, if requested by the sponsor. Details for the collection and evaluation of radiographic images are included in the Radiology Manual.

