7.7 Efficacy Analysis

7.7.1 Primary Efficacy Analyses:

The 2 primary efficacy endpoints of PFS and OS will be compared between CMB305 and placebo. Overall survival is defined as the time from randomization to the date of death.

Progression-free survival by investigator's assessment is defined as the time from randomization to the investigator-determined (using RECIST v1.1) date of disease progression or death. Radiographic images will be collected and assessed using RECIST v1.1 until the time the subject begins a new line of treatment.

For the purpose of PFS analysis, any one of the following events, whichever occurs first, will be used:

- Disease progression per RECIST v1.1 (See Appendix 1 [Table 7 \[Eisenhauer 2009\]](#))
- Symptomatic deterioration (global health deterioration) as described by RECIST v1.1
- For subjects with NED at time of randomization, any new malignant lesion that occurs after randomization per RECIST v1.1 (See Appendix 1 [Table 8](#))

Otherwise, subjects who do not have disease progression or have not died will be censored at the date when the last tumor imaging assessment determines a lack of progression. If a subject begins a new anti-cancer therapy or has radiotherapy, surgery, or other local regional therapy at a lesion site prior to documented progression, the subject will be censored at the last assessment where the subject was documented as progression free prior to the intervention. For subjects with NED at study entry, the appearance of a new malignant lesion as per RECIST v1.1 is defined as an event of progression for the purpose of PFS analysis. Subjects with 2 or more missing

response assessments (except for subjects with symptomatic deterioration) prior to a visit with documented progression (or death) will be censored at the last visit where the subject was documented to be progression free. PFS, by investigator's assessment, will be the primary PFS analysis. PFS by independent radiological review will be the supportive analysis.

The null hypothesis of no difference in OS/PFS between CMB305 and placebo, will be tested using a stratified log-rank test stratified by: disease status at screening (locally advanced unresectable versus metastatic), tumor response during screening (PR/SD versus CR/ NED), and by baseline presence of anti-NY-ESO-1 antibody (yes versus no)).

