APPENDIX 1: DETERMINATION OF TUMOR RESPONSE

Tumor response will be determined using RECIST v1.1 (Table 7) for subjects who enroll in the study with evidence of target and/or non-target lesions (Eisenhauer 2009). For subjects with NED at study entry RECIST v1.1 will be used such that the appearance of any new malignant lesion will be defined as PD, and no new lesions will be defined as SD as outlined in Table 8. Subjects with symptomatic deterioration will be documented as having had an event of PD as of the date the symptomatic deterioration was determined by the investigator.

Table 7 Time Point Response: Subjects with Target (+/- non-target) Disease

Target Lesion	Non-Target Lesion	New Lesion	Overall Response
CR	CR	No	CR
CR	Non-CR/non-PD	No	PR
CR	Non-evaluated	No	PR
PR	Non-PD or not all evaluated	No	PR
SD	Non-PD or not all evaluated	No	SD
Not all evaluated	Non-PD	No	NE
PD	Any	Yes or No	PD
Any	PD	Yes or No	PD
Any	Any	Yes	PD

CR – completed response; PR = partial response; SD = stable disease; PD = progressive disease; NE = inevaluable

Table 8 Disease Response Assessment on Study for Subjects with no Evidence of Disease at Study Day 1

Baseline		Post Day 1 Response Assessment			Overall Response
Target lesion	Non-Target lesion	Target lesion	Non-Target lesion	New Lesions	
Absent	Absent	Any	Any	New	PD
Absent	Absent	Absent	Absent	None	SD

PD = progressive disease; SD = stable disease

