## **8.2.2 Analysis of Primary Efficacy Variables**

### **8.2.2.1 Primary Analyses**

The null hypothesis of no difference in PFS/OS between CMB305 and placebo, in the ITT set, will be tested using a stratified log-rank test stratified by randomized stratification factors: disease status at screening (locally advanced unresectable versus metastatic), tumor response during screening (PR/SD versus CR/NED), and by baseline presence of anti-NY-ESO-1 antibody (yes versus no)).

The null hypothesis will be rejected and it will be concluded that PFS/OS on CMB305 is superior to that on placebo if the 1-sided p value at the final analysis for the stratified log-rank test is less than the pre-specified alpha as discussed in Multiplicity Section. Success for either of the 2 primary endpoints defines study success.

The Kaplan-Meier curve will summarize PFS/OS graphically by treatment arm. Tabular summaries of the Kaplan-Meier curves, including the median and 2-side 97.5% and 95% CI will be provided by treatment arm. The 4, 6, 8, and 10 month PFS rate and 12, 18, 24, and 30 month OS rate will be provided by treatment arm.

The associated HR and its 2-sided 97.5% and 95% CI will be provided using the stratified Cox proportional hazard model for PFS/OS, comparing treatment arm, stratified by the randomized stratification factors .

The final PFS analysis will be conducted when a total of 141 PFS events occur. The final OS analysis will be conducted when a total of 179 deaths occur.

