### **8.2.2.2 Sensitive Analysis of Primary Endpoints (PFS/OS)**

The sensitive analyses of primary endpoints will include:

- OS using the Safety set, according to the treated arm

- PFS by investigator assessment and OS using the EE set
- PFS by investigator assessment in the ITT set, with start of subsequent anti-cancer therapy as a PFS event
- PFS based on the IRC response assessment, if required, for both ITT and EE sets as supportive analysis
- Stratified Cox proportional hazard model for PFS or OS, in ITT set, with additional covariates of number of cycles in first line chemotherapy, and/or type of prior therapy (adjuvant/neoadjuvant chemotherapy and surgery and/or radiotherapy)
- PFS and OS by Fleming-Harrington weighted log-rank test with  $\rho = 0$ ,  $\gamma = 1$ , for adjustment of delayed effects.
- The Fleming-Harrington weight for late effects is defined as below
 
$$W_n(t) = (S_n(t))^{\rho} (1 - S_n(t))^{\gamma}$$
- PFS and OS by piecewise Cox proportional model in presence of non-proportional hazard for time-varying treatment effect:
 
$$h(t | z_i) = h_o(t) \exp(\alpha z_{1i} + \beta_1 z_{2i} 1(t \leq c_i) + \beta_2 z_{2i} 1(c_i < t \leq c_{i+1}) + \beta_3 z_{2i} 1(t > c_{i+1}))$$

Where  $Z_{1i}$  is time-independent covariates such as stratification factors;  $C_i$  and  $C_{i+1}$  are cut points (e.g. 4 and 8 months, respectively) for time period and  $I(\cdot)$  denotes the indicator function.
- PFS and OS not censoring events that occur after the cutoff.
- OS with competing events being taken into consideration. Competing events for death are “definite” lost to follow-up and withdrawal of consent for continued survival assessments. Both of these competing events are subject to revision for an individual subject with the passage of time. The cumulative incidence estimates will be plotted if the percent of subjects with competing events in either arm exceeds 3%.
- PFS with competing events being taken into consideration. Competing events for PFS event are lost to follow-up, withdrawal of consent, start of other anti-cancer therapy, or two or more missing scans prior to a PFS event. The cumulative incidence estimates will be plotted if the percent of subjects with competing events in either arm exceeds 3%.

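### SAP Table 3 omits the protocol's exemption, so symptomatic deterioration first recorded after two consecutive missed scans is censored instead of counted as a PFS event

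*SAP*

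**What the plan says.** **Protocol.** The missed-scan rule in the synopsis begins "Subjects with 2 or more missing response assessments (except for subjects with symptomatic deterioration) prior to a visit with documented progression", and section 7.7.1 repeats it with the same exemption. Section 6.3.1.3 says that subjects with symptomatic deterioration "will be considered as having PD at the time of documented global deterioration of health for the purpose of determining PFS". Appendix 1 agrees: they "will be documented as having had an event of PD as of the date the symptomatic deterioration was determined by the investigator".

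**SAP.** Section 5.1.1.1 lists among the investigator-determined PD events "Symptomatic deterioration (global health deterioration) as described by RECIST v1.1". The second row of Table 3 then censors "Investigator-determined PD or death after 2 or more consecutive missed tumor assessments" at the last adequate assessment without PD before the first missed one. It contains no exemption. The only carve-out for symptomatic deterioration in the text around Table 3 concerns PFS by independent review, where such deterioration is not counted as PD at all.

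**Precedence.** SAP section 9, which is the place for departures from the protocol, lists none and gives the SAP precedence where the two differ.

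**The concern.** PFS by investigator assessment is one of two primary endpoints, tested at 1-sided 0.0125. A subject who becomes too unwell to be scanned, misses two assessments and is then recorded as deteriorating has a PFS event under the protocol. Under the SAP the same subject is censored at the last clean scan, before the decline. The censoring follows from the subject's worsening condition, so the log-rank and Cox assumption of non-informative censoring is doubtful for exactly these subjects.

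The protocol's exemption has little purpose except in this situation. If deterioration is recorded before the scans are missed, it is already the first event in either document. The SAP therefore reverses the one case for which the exemption matters, and does so without saying so.

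**Working it through.** **1. Tracing one subject (illustrative dates on an 8-weekly schedule).**
- Clean scan at week 8, scans at weeks 16 and 24 missed, deterioration documented at week 26. Protocol: event at week 26. SAP second row: censored at week 8. A later death does not bring the subject back, because the row covers death as well.
- Clean scan at week 8, deterioration documented at week 14, later scans missed. Event at week 14 in both documents.

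The conflict is confined to the first pattern.

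**2. Does any analysis in SAP 8.2.2.2 restore the event?**
- Competing-events PFS: no. Its list of competing events includes "or two or more missing scans prior to a PFS event".
- Independent-review PFS: no. Symptomatic deterioration is excluded.
- Analysis that keeps events after the cutoff: no. It concerns the data cutoff date (SAP 8.2.1.1), not missed scans.
- EE-set PFS: no change to Table 3 is stated.
- New anti-cancer therapy counted as an event: only partly. A censored subject who later starts therapy might count, but at the therapy date, and the SAP does not say whether the missed-scan row still applies.

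None clearly restores the event at its documented date.

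**3. The plan's own event number.** Inputs from SAP section 4: HR 0.55, 1-sided alpha 0.0125, power 90%, 1:1 allocation.
- Schoenfeld: d = 4(z_alpha + z_beta)² / (ln HR)² = 4(2.241 + 1.282)² / (0.598)² = 139, close to the stated 141.
- Power at 141 = Φ(√141/2 × 0.598 − 2.241) = 90.5%.

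The sample-size figure stands, and the point does not depend on it.

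**4. How many of the 141 events could be eligible?** Assumptions: exponential PFS with medians 4 and 4/0.55 = 7.27 months; 124 per arm; 62 subjects enrolled uniformly in year 1 and 186 in year 2; no dropout.

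An event must come after two scans could have been missed. With scans every 8 weeks from Day 1 (Table 2, footnote l), that is week 16, or day 112 = 3.68 months. Share of all eventual events before then:
- placebo: 1 − 2^(−3.68/4) = 0.47
- CMB305: 1 − 2^(−0.55 × 3.68/4) = 0.30

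By simulation the 141st event comes at month 23.6 (81 placebo, 60 CMB305). The eligible count depends on two readings:

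| Window | Events of the 141 |
|---|---|
| After day 112, no upper limit | 58 |
| Day 112 to 365 | 52 (27 placebo, 25 CMB305) |
| Day 148 to 365 | 37 |

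Day 148 applies if imaging follows the Table 2 grid, which shows a scan at Day 64 and then at boost visits starting on Day 148. The day-365 limit applies if deterioration must involve stopping study treatment, as protocol 3.1.3 and 6.3.1.3 say. The event list in 7.7.1 and Appendix 1 do not repeat that condition.

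**5. Illustration of size.** The documents give no frequency, so an affected share of 2% to 10% of eligible events is assumed.
- Events censored: 0.02 × 37 = 0.7 to 0.10 × 58 = 5.8, or about 1 to 6.
- Delay if 141 is counted after Table 3: the next event comes about 2.4 days after the 141st, so 1 × 2.4 to 6 × 2.4, or about 2 to 14 days.
- HR, using the day 112 to 365 window and moving each affected event back to the last scan before the two missed ones: the mean shift runs from −0.012 (10% of CMB305 events, none on placebo) to +0.006 (10% of placebo events, none on CMB305). With 10% in both arms it is about −0.005. A single trial can move by up to about 0.05.

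**The case against.** **The SAP was written for another protocol version.** It cites v2.0, and the protocol supplied is v2.1 DK. The v2.1 log gives main revisions only and none concerns censoring, so it is an inference that v2.0 already held the exemption. This stands as a limit on saying that the SAP departed from its source. It does not remove the conflict between the two documents supplied.

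**The analyst has a rule.** Because the SAP takes precedence, programming is not ambiguous. That is correct, and the defect is an undeclared change to a primary-endpoint definition. Precedence makes the change effective without justifying it. OS is untouched.

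**Stronger readings that a reader might infer.**
- *All symptomatic deterioration is lost.* It is not; deterioration recorded before the second consecutive missed scan remains an event.
- *Power is lost.* SAP 8.2.2.1 says "The final PFS analysis will be conducted when a total of 141 PFS events occur", and a subject censored by Table 3 is not a PFS event, so the natural count is after censoring. Even if 141 were counted before the row is applied and 7 events were lost, the remaining 134 would give 88.9% power.
- *52 is a ceiling.* It is not firm in either direction, as the table in the working shows.

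**Conclusion.** The point holds as a minor but real inconsistency in the primary PFS definition. Deterioration first recorded after two consecutive missed scans is an event under the protocol and a censoring under the SAP, and the SAP does not declare the difference.

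The text comparison is certain for the documents supplied; that v2.0 had the same exemption is inferred. The size is uncertain: between about 37 and 58 of the 141 events are late enough to be eligible, on exponential PFS and the planned accrual, and most of those would be progression seen on a scan. The 2% to 10% share is an assumption without support in the documents. On that assumption the average HR shift is about 0.01 or less. Nothing here shows that the trial's conclusion would change. The reason to act is that the rule should be settled before unblinding, and that the SAP's version adds likely informative censoring.

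A related wording difference belongs in the same edit: the protocol counts two or more missing assessments, while the SAP requires them to be consecutive.

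**What to change.** In the second row of SAP Table 3 add: *except symptomatic deterioration, which is an event on the date it is documented (protocol 6.3.1.3 and Appendix 1), unless a subsequent intervention started first, in which case the third row applies*. The last clause is needed because otherwise a subject with two missed scans, then new therapy, then deterioration would be an event under the second row and censored under the third. The event date should be referenced to 6.3.1.3 and Appendix 1, since 7.7.1 gives the exemption but not the date.

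Use the same term, either *missing* or *consecutive missed*, in both documents.

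If the departure is intended, declare it with a reason in SAP section 9 and add a sensitivity analysis to 8.2.2.2 that counts these subjects as events on the documented date.

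Cost: one table row in the SAP and matching wording for the missed-scan rule in the protocol, or one entry in SAP 9 plus one extra PFS run. No new data are needed.

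### The missed-scan censoring rule for primary PFS is worded three ways, and none ties the gap to the event, so a well-dated progression can be censored (small effect)

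*SAP*

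**What the plan says.** **SAP 5.1.1.1, Table 3, second row.** The situation is "Investigator-determined PD or death after 2 or more consecutive missed tumor assessments". The censoring date is "Date of last adequate tumor assessment with no evidence of PD that is before the first missed assessment". The row has no exemption. The list of PD events in the same section includes "Symptomatic deterioration (global health deterioration) as described by RECIST v1.1", so the row applies to symptomatic deterioration too.

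**Protocol synopsis and 7.7.1.** The rule covers "Subjects with 2 or more missing response assessments (except for subjects with symptomatic deterioration) prior to a visit with documented progression (or death"). These subjects "will be censored at the last visit where the subject was documented to be progression free". The missing assessments need not be consecutive, and symptomatic deterioration is exempt.

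**SAP 8.2.2.2.** The competing-event sensitivity analysis of PFS lists as a competing event "or two or more missing scans prior to a PFS event". Consecutiveness is again not required.

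**Precedence.** SAP section 9 says that the SAP governs where the two documents differ. It does not list this rule as a change from the protocol.

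**The concern.** PFS by investigator assessment is one of the two primary endpoints. A missed-scan rule exists to avoid dating a progression to a scan that follows a long unobserved stretch. It serves that purpose only if the unobserved stretch is the one that ends in the event. If an adequate scan shows no progression after the gap, the gap says nothing about when the later progression occurred.

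None of the three wordings makes this link, and they differ on the trigger, the exemption and the censoring date. The same subject can therefore be an event in one document and censored in the other, or censored at dates 32 weeks apart. At stake are which subjects count as PFS events, when the 141st event is reached, and a loss of events that grows with follow-up and so is larger in the arm with longer PFS.

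**Working it through.** **1. The plan's own figure.** Inputs from SAP section 4: HR 0.55, one-sided alpha 0.0125, power 90%, 1:1 allocation. Schoenfeld: events = 4(2.2414 + 1.2816)² / (ln 0.55)² = 49.645 / 0.3574 = 138.9, so 139. The stated 141 gives 90.5% power. The event target is sound; the issue is which subjects count towards it.

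**2. The rules applied to the same scan histories.** Scans are every 8 weeks in the first year, with SD at every attended scan before the event. The last column is the rule proposed under the fix.

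| History | Protocol | SAP Table 3, literal | Gap must directly precede event |
|---|---|---|---|
| A. Weeks 16 and 32 missed, PD week 48 | Censored week 40 | Event week 48 | Event week 48 |
| B. Weeks 16 and 24 missed, SD weeks 32 and 40, PD week 48 | Censored week 40 | Censored week 8 | Event week 48 |
| C. Weeks 16 and 24 missed, symptomatic deterioration week 30 | Event week 30 | Censored week 8 | Censored week 8, unless exempted |
| D. Weeks 32 and 40 missed, PD week 48 | Censored week 24 | Censored week 24 | Censored week 24 |

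Only D gives the same answer throughout. In B the PD lies between weeks 40 and 48, a single scan interval, yet both documents discard it. The SAP also discards 40 − 8 = 32 weeks of documented progression-free time.

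**3. Why the loss grows with follow-up.** A PD first seen at week 48 has five earlier scans. The chance that at least two were missed, which triggers the protocol rule, is 1 − 0.95⁵ − 5(0.05)(0.95⁴) = 2.3% at a 5% miss rate, and 8.1% at 10%. A PD first seen at week 24 has only two earlier scans, so the chance is 0.05² = 0.25%, or 1% at 10%.

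**4. Size by simulation.** Inputs from the documents: placebo median PFS 4 months, HR 0.55 (CMB305 median 4/0.55 = 7.3 months), scans every 8 weeks and then every 12 weeks after 12 months. Assumptions: exponential PFS; independent misses at the same rate in both arms; progression found at the first attended scan after it occurs; no deaths or symptomatic deterioration. The documents give no miss rate, so two are shown. Percentage of progressions censored, placebo / CMB305:

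| Miss rate per scan | Protocol | SAP literal | Corrected rule |
|---|---|---|---|
| 5% | 1.8 / 4.0 | 0.8 / 1.2 | 0.5 / 0.6 |
| 10% | 6.3 / 12.4 | 3.3 / 4.9 | 2.1 / 2.4 |

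Repeat runs moved these by a few tenths of a point at most. The excess of the literal SAP rule over the corrected one is 0.3 / 0.6 points at 5% and 1.2 / 2.5 points at 10%. Applying the larger arm's excess to all 141 events gives an upper figure of 141 × 0.006 = 0.8 events at 5%, and 141 × 0.025 = 3.5 events at 10%. Protocol and SAP give different results (status or date) for 1.3% / 3.5% of progressions at 5%, and 4.3% / 10.0% at 10%.

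**5. Effect on the hazard ratio.** In a simulation on the same assumptions, the estimated HR under the literal SAP rule and the corrected rule was 0.592 and 0.591 at 5% misses, and 0.597 and 0.595 at 10%. The levels exceed 0.55 because scan dates tie many progressions together. Only the difference matters here: 0.001 to 0.002, towards the null.

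**The case against.** **The conflict is already settled.** SAP section 9 gives the SAP precedence, so history A has one governing answer, an event. This stands, and the protocol-rule percentages above therefore describe a rule that does not govern the analysis. Precedence does not supply the missing link between gap and event in Table 3, nor does it settle the difference between Table 3 and SAP 8.2.2.2.

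**The ordinary reading of Table 3 is one gap leading straight to the event.** That is probably what was meant, and a careful programmer might code it so. The text does not say it, and the literal reading is open to anyone who follows the words. The SAP's stated purpose is to fix such choices before database lock.

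**A reader might infer a loss of power.** If 7 of 141 events (5%) were lost and not replaced, the Schoenfeld formula would give 88.9% at 134 events. The documents do not support this. Both set the final PFS analysis at 141 PFS events, and a progression censored by the rule is not one of them. With 248 subjects randomized there is room to wait for replacements, so the cost is time. A 5% loss is also well above the 0.8% / 1.2% found for the literal SAP rule at a 5% miss rate.

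**A reader might infer bias in favour of CMB305.** Nothing here shows it. With equal miss rates and no treatment effect, the rule treats the arms alike. With the planned effect, the shift in HR is negligible and towards the null. Unequal miss rates were not modelled, and the documents give no basis for choosing them.

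**Conclusion.** The rule is wrong as written, and the effect is small. Protocol 7.7.1 and the synopsis, SAP Table 3 and SAP 8.2.2.2 state three different missed-scan rules for a primary endpoint. The governing one, read literally, censors a progression dated to a single 8-week interval because of an earlier gap that a later scan had closed.

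At an assumed 5% to 10% miss rate, the literal SAP rule censors about 0.8% to 3.3% of placebo and 1.2% to 4.9% of CMB305 progressions; the corrected rule censors 0.5% to 2.1% and 0.6% to 2.4%. The consequences are which subjects count as events, the timing of the 141st event, and a somewhat larger loss in the arm with longer PFS. The percentages rest on exponential PFS at the planned medians and on random, equal misses. The conflict in wording rests on the texts alone.

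The listed sensitivity analyses do not cover the gap. None counts a PD or death after missed scans as an event. The competing-event analysis only reclassifies these subjects, with cumulative incidence plots if competing events exceed 3% in either arm. The analysis that leaves later events uncensored concerns the data cutoff, not missed scans.

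**What to change.** Put one rule in SAP Table 3, SAP 8.2.2.2, protocol 7.7.1 and the protocol synopsis:

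- Censor only when two or more consecutive scheduled assessments were missed immediately before the PD or death, with no adequate assessment in between.
- Censor at the last adequate assessment before that gap.
- State that an earlier gap followed by an adequate assessment has no effect.

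State in both documents whether symptomatic deterioration is exempt from this rule. At present the protocol exempts it and the SAP does not, and history C turns on the answer.

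Add one sensitivity analysis that counts PD or death as an event on its documented date, regardless of missed scans.

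The cost is a few sentences in the two documents and one further run of the PFS analysis. No data collection or sample size changes. The text should be settled before database lock and before the 141 PFS events are counted, because the rule decides which progressions enter that count.
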